**Table 7.2.4.2. CFB in IGA (without imputation)**

Domain	CFB in Proportion at Week 4 N=xx	p- value	CFB in Proportion at Week 8 N=xx	p- value	CFB in Proportion at Week 12 N=xx	p- value
IGA (Overall, how is the patient's facial acne right now?)						
Clear / Almost clear	%	p	%	p	%	p
Moderate / Severe	%	p	%	p	%	p
Mild	%		%		%	

Note: Data from Clinician DCF; X patients had missing data;

**Table 7.2.4.3. Facial IGA Success (without imputation)**

Character	Week 12
IGA Success	N=x
No	n (%)
Yes	n (%)

Note: Facial IGA success at Week 12, defined as a 2-point decrease in IGA score from baseline and a score of 0 (clear) or 1 (almost clear) at Week-12. The denominator for the percentages is the number of patients with available data (N=X)

**Table 7.2.4.4. Clinician Acne Evaluation (IGA) (with LOCF imputation)**

Character	Baseline (N=xx)	Week 4 (N=xx)	Week 8 (N=xx)	Week 12 (N=xx)
Overall, how is the patient's facial acne right now? (IGA)	S9A N, Mean (SD), Median, Min, Max	P2 N, Mean (SD), Median, Min, Max	P2 N, Mean (SD), Median, Min, Max	P2 N, Mean (SD), Median, Min, Max
Clear (0)	n (%)	n (%)	n (%)	n (%)
Almost clear (1)	n (%)	n (%)	n (%)	n (%)
Mild (2)	n (%)	n (%)	n (%)	n (%)
Moderate (3)	n (%)	n (%)	n (%)	n (%)
Severe (4)	n (%)	n (%)	n (%)	n (%)
Clear/almost clear	n (%)	n (%)	n (%)	n (%)
Moderate / Severe	n (%)	n (%)	n (%)	n (%)
Mild	n (%)	n (%)	n (%)	n (%)

**Table 7.2.4.5 Sub-group Analysis of IGA (with LOCF imputation)**

	% Clear/Almost Clear			
	Weeks			
	Baseline (N=x)	Week 4 (N=x)	Week 8 (N=x)	Week 12 (N=x)
Sex				
Male	n (%)	n (%)	n (%)	n (%)
Female	n (%)	n (%)	n (%)	n (%)
p-value	p	p	p	p
Age Group				
≥ 9 and < 12 years	n (%)	n (%)	n (%)	n (%)
≥ 12 and < 18 years	n (%)	n (%)	n (%)	n (%)
≥ 12 years	n (%)	n (%)	n (%)	n (%)
p-value	p	p	p	p
Race				
White	n (%)	n (%)	n (%)	n (%)
African	n (%)	n (%)	n (%)	n (%)
American/Black	n (%)	n (%)	n (%)	n (%)
Other	n (%)	n (%)	n (%)	n (%)
p-value	p	p	p	p
Body mass index				
< 25 kg/m 	n (%)	n (%)	n (%)	n (%)
≥ 25 kg/m 	n (%)	n (%)	n (%)	n (%)
p-value	p	p	p	p
Baseline facial IGA				
Moderate	n (%)	n (%)	n (%)	n (%)
Severe	n (%)	n (%)	n (%)	n (%)
p-value	p	p	p	p
Female who used oral contraceptive*				
Used	n (%)	n (%)	n (%)	n (%)
Did not use	n (%)	n (%)	n (%)	n (%)
p-value	p	p	p	p

Note: Data from Clinician DCF; X patients had missing data; The denominator for the percentages is the number of patients with available data (N=X)

\* The denominator for the percentages is the number of 'female' patients with available data (N=X)

**Table 7.2.4.6. CFB in IGA (with LOCF imputation)**

Domain	CFB in Proportion at Week 4 N=xx	p- value	CFB in Proportion at Week 8 N=xx	p- value	CFB in Proportion at Week 12 N=xx	p- value
IGA (Overall, how is the patient's facial acne right now?)						
Clear / Almost clear	%	p	%	p	%	p
Moderate / Severe	%	p	%	p	%	p
Mild	%		%		%	

Note: Data from Clinician DCF; X patients had missing data; The denominator for the percentages is the number of patients with available data (N=X)

**Table 7.2.4.7. Facial IGA Success (with LOCF imputation)**

Character	Week 12
IGA Success	N=x
No	n (%)
Yes	n (%)

Note: Facial IGA success at Week 12, defined as a 2-point decrease in IGA score from baseline and a score of 0 (clear) or 1 (almost clear) at Week-12. The denominator for the percentages is the number of patients with available data (N=X)

**Table 7.2.4.8. Sub-group Analysis of Facial IGA Success (with LOCF imputation)**

% IGA Success		Week 12 (N=x)
Sex		
Male	n (%)	
Female	n (%)	
p-value	p	
Age Group		
≥ 9 and < 12 years	n (%)	
≥ 12 and < 18 years	n (%)	
≥ 12 years	n (%)	
p-value	p	
Race		
White	n (%)	
African America/Black	n (%)	
Other	n (%)	
p-value	p	
Body mass index		
< 25 kg/m 	n (%)	
≥ 25 kg/m 	n (%)	
p-value	p	
Baseline facial IGA		
Moderate	n (%)	
Severe	n (%)	
p-value	p	
Female who used oral contraceptive*		
Used	n (%)	
Did not use	n (%)	
p-value	p	

Note: Data from Clinician DCF; X patients had missing data; The denominator for the percentages is the number of patients with available data (N=X).

\* The denominator for the percentages is the number of 'female' patients with available data (N=X)

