## 6.3 General Statistical Procedures

### 6.3.1 Overview

Data from Site Investigators and study Subjects will be treated separately, and combined into one dataset, based on the study assessments of interest. Validated instruments will be scored according to developer guidelines, reporting domain scores and overall summary scores, as appropriate. Home-grown questions/items will be analyzed and reported individually, based on the respective response scales. Change from Baseline (CFB) in scores (for continuous variables) or proportions (for discrete variables) will be computed as Week-12 minus Baseline measure for respective question responses.

Discrete measures will be assessed using summary statistics encompassing percentage of Subjects reporting particular outcome measures. The statistical differences in discrete variables to compare different patient groups (for subgroup analysis) for a given measure at a particular timepoint (such as Baseline or Week-12), or CFB in proportion of patients reporting a particular response to an outcome measure at a particular timepoint (such as Week-12) will be assessed using a  $\chi^2$  test. In case of likert scales, to compute P-values for CFB in proportions, the top-two response categories (of a likert scale) for a given question at Baseline will be grouped together into a single group proportion (versus the rest of the population/responders all together) and compared to the same group proportion at Week-12; the procedure will be repeated for the bottom-two response categories (of a likert scale) for a given question, by grouping them together into a single group proportion and compare it to the same group proportion at Week-12. For example, for ASIS item # 1 (how oily is your face right now), proportion of patients reporting “Not at all/A little” at Baseline will be grouped together (vs. rest of the population/responders) and compared to proportion of patients reporting “Not at all/A little” at Week-12; similarly, proportion of patients reporting “Quite a bit/Very” at Baseline will be grouped together and compared to proportion of

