## 6.5 Secondary Endpoint Analysis

The secondary endpoint of the study is the proportion of Subjects with Facial IGA success at Week 12, defined as  $\geq 2$ -point decrease in IGA score from baseline and a score of 0 (clear) or 1 (almost clear) at Week 12. The analyses of IGA success will be conducted for the overall cohort (using the FAS dataset). LOCF data imputation method will be used to impute responses at Week 12 for the Subjects with missing data at Week 12. Relationship between this endpoint (with LOCF imputation) and subject characteristics will be explored using descriptive analyses, by leveraging subgroup analysis outlined in Section 6.3.2.

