**Table 7.1.7.3. Sub-group analysis of EPQ 3**

**AH3:** How often do you think about your acne? Subjects who selected Never/Rarely.

	Baseline (N=x)	Week 12 (N=x)
Sex		
Male	n (%)	n (%)
Female	n (%)	n (%)
p-value	p	p
Age Group		
≥ 9 and < 12 years	n (%)	n (%)
≥ 12 and < 18 years	n (%)	n (%)
≥ 12 years	n (%)	n (%)
p-value	p	p
Race		
White	n (%)	n (%)
African America/Black	n (%)	n (%)
Other	n (%)	n (%)
p-value	p	p
Body mass index		
< 25 kg/m 	n (%)	n (%)
≥ 25 kg/m 	n (%)	n (%)
p-value	p	p
Baseline facial IGA		
Moderate	n (%)	n (%)
Severe	n (%)	n (%)
p-value	p	p
Female who used oral contraceptive*		
Used	n (%)	n (%)
Did not use	n (%)	n (%)
p-value	p	p

Note: The denominator for the percentage is the number of subjects with available data who selected Never/Rarely (N=X for baseline and N=X for week 12).

\*The denominator for the percentage is the number of 'female' subjects with available data who selected Never/Rarely (N=X for Baseline and N=X for Week-12).

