**Table 7.1.16.1 Sub-group Analysis of Patient Acne Severity (ASIS 9) (with LOCF)**

	% Clear / Almost clear				Weeks			
	Baseline	Week 4	Week 8	Week 12				
Sex								
Male	n (%)	n (%)	n (%)	n (%)				
Female	n (%)	n (%)	n (%)	n (%)				
p -value	p	p	p	p				
Age Group								
≥ 9 and < 12 years	n (%)	n (%)	n (%)	n (%)				
≥ 12 and < 18 years	n (%)	n (%)	n (%)	n (%)				
≥ 18 years	n (%)	n (%)	n (%)	n (%)				
p -value	p	p	p	p				
Race								
White	n (%)	n (%)	n (%)	n (%)				
African	n (%)	n (%)	n (%)	n (%)				
America/Black								
Other	n (%)	n (%)	n (%)	n (%)				
p -value	p	p	p	p				
Body mass index								
< 25 kg/m 	n (%), Mean	n (%), Mean	n (%), Mean	n (%), Mean				
≥ 25 kg/m 	n (%), Mean	n (%), Mean	n (%), Mean	n (%), Mean				
p -value	p	p	p	p				
Baseline facial IGA								
Moderate	n (%)	n (%)	n (%)	n (%)				
Severe	n (%)	n (%)	n (%)	n (%)				
p -value	p	p	p	p				
Female who used oral contraceptive*								
Used	n (%)	n (%)	n (%)	n (%)				
Did not use	n (%)	n (%)	n (%)	n (%)				
p -value	p	p	p	p				

\*The denominator for the percentage is the number of 'female' patients with available data (N=X).

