**Table 7.1.16.2 Sub-group Analysis of How Face Looks (ASIS 10) (with LOCF)**

	% Excellent/Very good				Weeks
	Baseline	Week 4	Week 8	Week 12	
Sex					
Male	n (%)	n (%)	n (%)	n (%)	n (%)
Female	n (%)	n (%)	n (%)	n (%)	n (%)
p-value	p	p	p	p	p
Age Group					
≥ 9 and < 12 years	n (%)	n (%)	n (%)	n (%)	n (%)
≥ 12 and < 18 years	n (%)	n (%)	n (%)	n (%)	n (%)
≥ 12 years	n (%)	n (%)	n (%)	n (%)	n (%)
p-value	p	p	p	p	p
Race					
White	n (%)	n (%)	n (%)	n (%)	n (%)
African	n (%)	n (%)	n (%)	n (%)	n (%)
America/Black					
Other	n (%)	n (%)	n (%)	n (%)	n (%)
p-value	p	p	p	p	p
Body mass index					
< 25 kg/m 	n (%), Mean	n (%), Mean	n (%), Mean	n (%), Mean	n (%), Mean
≥ 25 kg/m 	n (%), Mean	n (%), Mean	n (%), Mean	n (%), Mean	n (%), Mean
p-value	p	p	p	p	p
Baseline facial IGA					
Moderate	n (%)	n (%)	n (%)	n (%)	n (%)
Severe	n (%)	n (%)	n (%)	n (%)	n (%)
p-value	p	p	p	p	p
Female who used oral contraceptive					
Used	n (%)	n (%)	n (%)	n (%)	n (%)
Did not use	n (%)	n (%)	n (%)	n (%)	n (%)
p-value	p	p	p	p	p

Note: X patients had missing data; The denominator for the percentage is the number of patients with available data (N=X).

\*The denominator for the percentage is the number of 'female' patients with available data (N=X).

Table 7.1.17. Impact on Parents/Caregiver

Domain	Baseline	Week 12
Q2: Do you feel that you understand your child's acne-related concerns?	N Mean (SD), Median, Min, Max	N Mean (SD), Median, Min, Max
Not at all (0)	n (%)	n (%)
A little (1)	n (%)	n (%)
Somewhat (2)	n (%)	n (%)
Quite a bit (3)	n (%)	n (%)
Very much (4)	n (%)	n (%)
Q3: Over the past 7 days, how concerned have you been about your child's acne?	N Mean (SD), Median, Min, Max	N Mean (SD), Median, Min, Max
Not at all (0)	n (%)	n (%)
Slightly (1)	n (%)	n (%)
Somewhat (2)	n (%)	n (%)
Moderately (3)	n (%)	n (%)
Extremely (4)	n (%)	n (%)
Q4: How concerned are you about your child's ability to accomplish future goals and reach full potential due to acne?	N Mean (SD), Median, Min, Max	N Mean (SD), Median, Min, Max
Not at all (0)	n (%)	n (%)
Slightly (1)	n (%)	n (%)
Somewhat (2)	n (%)	n (%)
Moderately (3)	n (%)	n (%)
Extremely (4)	n (%)	n (%)

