Note: Data from Clinician DCF. Percentages are based on the total sample within respective groups.

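### Read literally, the notes to the subgroup response tables divide every row by the whole cohort (or by all females), so the printed percentages would be cohort shares and not subgroup rates

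*SAP*

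**What the plan says.** - **Table 7.2.4.8 (IGA success)** has one Week 12 column with a single N, cells of n (%), and a p-value under each factor. Its general note reads "The denominator for the percentages is the number of patients with available data (N=X"). Its starred note covers both contraceptive rows, *Used* and *Did not use*: "The denominator for the percentages is the number of 'female' patients with available data (N=X").
- **Tables 7.2.4.5 (IGA clear or almost clear) and 7.2.9 (investigator satisfaction)** carry the same two notes.
- **Table 7.1.16.2 (ASIS item 10)** has the pair in the singular, beginning "The denominator for the percentage is the number of patients with available data (N=X").
- **Table 7.1.16.1 (ASIS item 9)** prints only the female note, "The denominator for the percentage is the number of 'female' patients with available data (N=X"). Its other rows have no stated denominator.
- **Tables 7.1.7.1 to 7.1.7.11 (EPQ subgroups)** use a different base. In Table 7.1.7.3, for example: "The denominator for the percentage is the number of subjects with available data who selected Never/Rarely". The starred version restricts this to female responders.
- **The text on purpose and test:** SAP 6.3.1 assigns a chi-square test to "The statistical differences in discrete variables to compare different patient groups (for subgroup analysis) for a given measure at a particular timepoint". SAP 6.5 says "Relationship between this endpoint (with LOCF imputation) and subject characteristics will be explored using descriptive analyses", and 6.6.1 sets the same aim for investigator satisfaction.

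SAP 6.3.1, 6.3.2, 6.5 and 6.6.1 do not define a within-subgroup denominator that would override the table notes.

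**The concern.** A reader will take a male row under a heading of percent IGA success as the success rate among males. The note instead gives one cohort-level denominator, and the starred note gives one all-female denominator to two rows that split the females. A table programmed from those notes would print a quantity that depends on subgroup size as well as response. It could show a gap where there is none, or reverse a real one. It would also sit beside a p-value that answers a different question, because the chi-square test compares rates between groups.

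Table 7.2.4.8 is the display of the secondary endpoint by the subgroups listed in SAP 6.3.2, and Table 7.2.9 does the same for satisfaction. The study is descriptive, so these percentages are what will be read and quoted.

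**Working it through.** The plan has no figure to reproduce here: the tables are empty shells and no subgroup sizes or rates are given. The sizes and rates below are assumptions, chosen to show how the two readings differ.

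**Formulas.** For subgroup g, let n_g be the patients with data, s_g the responders, and N the patients with data in the whole column.

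- Within-group rate: r_g = s_g / n_g
- Percentage under the literal note: s_g / N = (n_g / N) × r_g
- Contraceptive rows: the same, with N replaced by all females with data

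The literal figure is therefore the rate scaled by the subgroup's share. If group 1 has the higher rate, the printed order reverses whenever n_2 / n_1 exceeds r_1 / r_2.

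| Assumed case | Row | s_g / n_g | Within-group rate | Literal note |
|---|---|---|---|---|
| Equal rates, N = 250, 60% female | Male | 60/100 | 60.0% | 60/250 = 24.0% |
| | Female | 90/150 | 60.0% | 90/250 = 36.0% |
| Baseline IGA, N = 250 | Moderate | 100/200 | 50.0% | 100/250 = 40.0% |
| | Severe | 35/50 | 70.0% | 35/250 = 14.0% |
| Contraceptives, 150 females, equal rates | Used | 27/45 | 60.0% | 27/150 = 18.0% |
| | Did not use | 63/105 | 60.0% | 63/150 = 42.0% |
| Contraceptives, 150 females, unequal rates | Used | 30/50 | 60.0% | 30/150 = 20.0% |
| | Did not use | 40/100 | 40.0% | 40/150 = 26.7% |

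**Range for the first case.** With 60% success in both sexes, the literal rows (male, female) are 30.0% and 30.0% at 50% female, 24.0% and 36.0% at 60%, and 18.0% and 42.0% at 70%. The result is the same for N = 200, 250 and 300. The false gap depends only on the imbalance in group size.

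**Against the p-value.** The Pearson chi-square on the subgroup-by-response counts gives p = 1.00 in the first case, next to a printed 12-point gap. In the baseline IGA case it gives p = 0.011 for a true 50.0% versus 70.0%, next to rows that point the other way. Here the size ratio is 200/50 = 4 and the rate ratio is 70/50 = 1.4, so the reversal condition is met.

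**EPQ tables.** These divide by responders, so the rows describe who the responders are. Assume 100 males and 150 females. If 20% of each choose the favourable response at baseline, the rows are 20/50 = 40% and 30/50 = 60%. If 60% of each choose it at Week 12, they are 60/150 = 40% and 90/150 = 60%. The response rate has tripled and the printed percentages have not moved.

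**The case against.** The strongest reply is that the general note is template text about missing data. It appears under non-subgroup tables as well, usually after the count of patients with missing data, and it may mean only that such patients are left out. The headings, the between-group p-values and the aims in SAP 6.5 and 6.6.1 all point to within-group rates. This stands as evidence of intent, and within-group rates were probably meant. It does not change what the notes say, and a programmer works from the notes.

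A reader might infer that the starred note rules out a row-by-row reading, since it would otherwise be unnecessary. The documents do not go that far. The note may serve only to keep males out of the non-user row. It also appears under Table 7.1.11, whose cells are n and mean with no percentages, so it was at least partly copied. Nor is much proved by the note to Table 7.4.5, "Percentages are based on the total sample within respective groups": the groups there are columns, not row subgroups. The EPQ notes weigh more. They sit in shells of the same layout and explicitly set a base that is not the subgroup.

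Four further inferences should be resisted:

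- **That the rows always add up to the overall rate.** The contraceptive rows would add up to the female rate. The age rows in Table 7.2.4.8 overlap as labelled (12 to under 18, and 12 and over).
- **That every row of Table 7.1.16.1 is put over all patients.** Only its contraceptive rows have a stated denominator.
- **That Table 7.2.4.8 is the only stratified display of IGA success.** Table 7.5.1 also stratifies it, by visit type.
- **That the tests or the secondary endpoint are wrong.** The chi-square test works on counts, the p-values are declared exploratory, and the overall result in Tables 7.2.4.3 and 7.2.4.7 is untouched.

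Some rates could also be recovered approximately from group sizes shown elsewhere, such as gender in Table 7.2.3 and baseline IGA in Table 7.2.4.1. Counts by BMI group are not shown in another shell.

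**Conclusion.** The point holds as a wrong stated rule in the table notes. Taken literally, the notes to Tables 7.1.16.2, 7.2.4.5, 7.2.4.8 and 7.2.9, and the starred note to Table 7.1.16.1, produce shares of the cohort or of all females. Those shares cannot show how response relates to subject characteristics. The size of the distortion depends on group imbalance: it is nil between equal groups and can reverse the order between unequal ones, as in the assumed 60% versus 40% that prints as 20.0% versus 26.7%. The EPQ subgroup tables have a related fault on items that belong to the primary endpoint.

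The conclusion rests on the literal reading, and the illustrations rest on assumed sizes and rates. It affects only the subgroup percentages. The documents do not show that any table has been produced this way.

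**What to change.** 1. In the notes to Tables 7.1.16.2, 7.2.4.5, 7.2.4.8 and 7.2.9, state that each row is divided by the number of patients in that subgroup with data at that timepoint.
2. Replace the starred all-female denominator, including in Table 7.1.16.1, with two denominators: female users with data and female non-users with data.
3. Add the row-level note to Table 7.1.16.1 for its other rows, which now have none.
4. Make the same correction in Tables 7.1.7.1 to 7.1.7.11, so that each row gives the proportion of that subgroup choosing the response.
5. Print n/N in every row so that the base is visible.

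The cost is a change of note wording and about one programming line per table. It needs no new data, and the counts and tests do not change. If any of these tables has already been run, check which denominator was used.

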**Table 7.2.5. Seysara Treatment Characteristics**

Character	Baseline (N=x)	Week 4 (N=x)	Week 8 (N=x)	Week 12 (N=x)
Prescription dose	(M12.1)	(P13A1)	(P13A1)	(P13A1)
60 mg	n (%)	n (%)	n (%)	n (%)
100 mg	n (%)	n (%)	n (%)	n (%)
150 mg	n (%)	n (%)	n (%)	n (%)
Prescription frequency	(M12.2)	(P14A1)	(P14A1)	(P14A1)
Once daily	n (%)	n (%)	n (%)	n (%)
Other 1	n (%)	n (%)	n (%)	n (%)
Other 2	n (%)	n (%)	n (%)	n (%)

**Table 7.2.6.1 Prior Acne Treatment (ever tried) Including Within the Past 6 Months**

Character	Baseline (N=x)
Has not use any acne medication	n (%)
Topical medication	
Topical retinoids	n (%)
Salicylic acid	n (%)
Benzoyl peroxide	n (%)
Topical antibiotics	n (%)
Topical Dapsone	n (%)
Azelaic acid	n (%)
Topical Clascoterone	n (%)
Other (total)	n (%)
A	n (%)
B	n (%)
C	n (%)
Oral medication	
Oral antibiotics (tetracycline or macrolide)	n (%)
Anti-androgen agents	n (%)
Oral antibiotics (non-tetracycline class)	n (%)
Isotretinoin	n (%)
Other	
A	n (%)
B	n (%)
C	n (%)
Oral contraceptives (any type)	n (%)
Other therapies	
Light therapy	n (%)
Drainage and extraction	n (%)
Chemical peel	n (%)
Steroid injection	n (%)
Other	n (%)

Note: Data from Clinician DCF; X patients had missing data; The denominator for the percentages is the number of patients with available data (N=X)  
(Programmer's note: this is a combination of internal Avant tables 7.2.6.x1 & 7.2.6.x2)

**Table 7.2.6.2 Acne Concomitant Medication Use**

Character	N=X
Has not use any acne medication	n (%)
Topical medication	
Topical retinoids	n (%)
Salicylic acid	n (%)
Benzoyl peroxide	n (%)
Topical antibiotics	n (%)
Topical Dapsone	n (%)
Azelaic acid	n (%)
Topical Clascoterone	n (%)
Other (total)	n (%)
A	n (%)
B	n (%)
C	n (%)
Oral medication	
Oral antibiotics (tetracycline or macrolide)	n (%)
Anti-androgen agents	n (%)
Oral antibiotics (non-tetracycline class)	n (%)
Isotretinoin	n (%)
Other	n (%)
A	n (%)
B	n (%)
C	n (%)
Oral contraceptives (any type)	n (%)
Other therapies	
Light therapy	n (%)
Drainage and extraction	n (%)
Chemical peel	n (%)
Steroid injection	n (%)
Other	n (%)

Note: Data from Clinician DCF; X patients had missing data; The denominator for the percentages is the number of patients with available data (N=X)

**Table 7.2.7. Non-Acne Concomitant Medication Use**

**Non-Acne concomitant medication use during any time of the study**

**M15:** Is the patient currently taking any concomitant medications to manage conditions other than acne?

**M15Ar1**

**<<categories from WHO ATC classifications>>**

A	n (%)
B	n (%)
C	n (%)
D	n (%)
E	n (%)

Note: Data from Clinician DCF; X patients had missing data; The denominator for the percentages is the number of patients with available data (N=X). This concomitant non-Acne medication use correspond to use of medications at any time during the study observation period, overlapping with Seysara medication use.

**Table 7.2.8. Physician Satisfaction with Seysara**

	Week 12 (N=x)
FP2: How satisfied are you with sarecycline/Seysara® treatment outcomes?	N, Mean (SD), Median, Min, Max
Very Satisfied (5)	n (%)
Satisfied (4)	n (%)
Neutral (3)	n (%)
Dissatisfied (2)	n (%)
Very Dissatisfied (1)	n (%)
Very Satisfied/Satisfied	n (%)
Dissatisfied/Very Dissatisfied	n (%)
Neutral	n (%)

Note: Data from Clinician DCF; X patients had missing data; The denominator for the percentages is the number of patients with available data (N=X).

**Table 7.2.9. Subgroup analysis: Physician Satisfaction with Seysara**

% Very Satisfied/Satisfied		Week 12 (N=x)
Sex		
Male	n (%)	
Female	n (%)	
p-value	p	
Age Group		
≥ 9 and < 12 years	n (%)	
≥ 12 and < 18 years	n (%)	
≥ 12 years	n (%)	
p-value	p	
Race		
White	n (%)	
African America/Black	n (%)	
Other	n (%)	
p-value	n (%)	
		p
Body mass index		
< 25 kg/m 	n (%)	
≥ 25 kg/m 	n (%)	
p-value	p	
Baseline facial IGA		
Moderate	n (%)	
Severe	n (%)	
p-value	p	
Female who used oral contraceptive*		
Used		
Did not use	n (%)	
p-value	n (%)	
		p

Note: Data from Clinician DCF; X patients had missing data; The denominator for the percentages is the number of patients with available data (N=X).

\*The denominator for the percentages is the number of 'female' patients with available data (N=X).

